5.2 PRIMARY OBJECTIVES

To establish whether children’s mean length of utterance during educator interactions is impacted by educator participation in the Training *and* whether early childhood educators participating in the Training demonstrate a greater change in their use target interaction skills when interacting with children in their care within a training period compared to a period of no training.

5.3 SECONDARY OBJECTIVES

Secondary objectives of the current research include determining the change in children’s linguistic productivity (number of words said, number of conversational initiations, and number of conversational turns) and complexity (vocabulary diversity) during periods when their educator is, and is not, attending the Training. All objectives will be achieved through observation of educator/child interactions at four time points (Time 2-5 described in section 5.6.1).

5.4 OUTCOME MEASURES

This research includes two primary outcome measures: (1) mean length of utterance¹ demonstrated by the child, and (2) a composite score of overall interaction strategies demonstrated by the target educator. These measures are consistent with previous research investigating children’s language development and adult-child interactions (Girolametto, Weitzman, & Greenberg, 2003; Girolametto, Sussman, & Weitzman, 2007; Piasta et al, 2012).

The outcome measures for the current study will be gathered from four 15-minute interactions between educator-child dyads collected before and after each training period. A difference score for each outcome measure will be calculated for each stage of training (differences between Time 2 and

¹ Mean length of utterance is a well-established measure of child language first described by Brown (1973). The calculation of mean length of utterance is based on the average number of morphemes produced per child utterance. It is an appropriate measure of language for young children (Ezeizabarrena & Fernandez, 2018).

Time 3 will produce Difference Score 1; change between Time 4 and Time 5 will produce Difference Score 2; time points are described in Figure 1 below).

Primary Outcome Measures:

The primary outcome measure for educators will be the change in the composite score of overall interaction strategies demonstrated by the target educator in a 15-minute interaction with a child during a training period and during a period of no training. Eight target interaction strategies were defined by Speech Pathologists in WSLHD, with reference to the Teacher Interaction and Language Rating Scale (TILRS; Girolametto, Weitzman, & Greenberg, 2000) and the Conversational Responsiveness Assessment and Fidelity Tool (CRAFT; Friel, Wiggins, & Justice, 2007). Target interaction skills include three Child-oriented strategies, two Interaction-promoting strategies and three Language-modeling strategies. **Child-oriented strategies** include: (1) Encourages child to initiate by observing, waiting expectantly and listening, (2) Responds to the child's initiation with animation and specific language, and (3) Adjusts their position so that they are face to face with the child. **Interaction-promoting strategies** include: (4) Uses a variety of questions to stimulate conversations, and (5) Encourages turn taking. **Language-modeling strategies** include: (6) Uses a variety of vocabulary, (7) Expands the child's utterances by recasting and adding ideas, and (8) Extends the child's utterances by giving information about the topic. Each of these eight strategies will be coded as 'absent' (0) or 'present' (1) for each 30 second segment of the 15-minute interaction. An average will be taken for each strategy across all segments of the video. Then, all average scores will be summed to create a composite score of use of interaction strategies by educators. The presence of these skills will be coded by two members of the research team. These two members will score two video samples independently and meet to reach consensus on the presence of each strategy based on these two videos. The remaining video samples will be randomly allocated and coded by one of these two researchers; each of the two researchers will code 50% of the video samples each. Inter- and intra-rater reliability will be calculated based on 10% of the recorded samples.

The Primary outcome measure for children will be the change in mean length of utterance within a 15-minute interaction with an educator during an educator training period compared to a period of no training.

Secondary Outcome Measures:

The secondary outcome measures for educators will be the difference in the frequency with which the educator uses each of the target interaction strategies in the 15-minute interaction with a child. Target interaction strategies are listed above in Primary Outcome Measures. Difference scores for each of these average scores of presence or absence of the strategy will be compared.

The secondary outcome measures for children will be difference scores for four measures of linguistic productivity or 'talkativeness': (1) total number of words said, (2) number of communication initiations, (3) number of conversational turns, and (4) vocabulary diversity (a measure of linguistic complexity). These will be obtained via computerised conversational language analysis of the 15-minute interaction with an educator. Difference scores for each of these measures will be calculated and compared.

Study Design

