6.2.1 Educator inclusion criteria

Inclusion criteria for educators will include consent to participate in all stages of the study and anticipated completion of the Training program. No limitations on Educator participation will be made based on prior training or level of education. Routine early childhood educator training at both TAFE and University levels does not cover the content of the Training provided as

described for the current study. Group comparisons will be conducted at baseline to ensure homogeneity in group variability based on level of Education.

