6.2.2 Child inclusion criteria

The inclusion criteria for child participants are: (1) aged 24-42 months and attend the consenting educator's ECEC at least one day per week, (2) no parental concerns about speech and/or language development, (3) no concerns identified based on the child's performance on the Communication section of the Ages and Stages Questionnaire (ASQ; Squires, Bricker & Twombly, 2009) (Appendix D) completed with a parent in an initial phone call, and (4) no concerns identified based on the Preschool Language Scales Screener (PLS; Zimmerman, Steiner, & Pond, 2011) (Appendix C) completed with a speech pathologist via videoconference at the child's ECEC. Eligibility will be confirmed after consent has been received from interested parents and the child's screening has been completed at the centre.

The ASQ screens children for concerns about overall development and can be a first step to identify children who require further evaluation for developmental concerns. It is a parent evaluation checklist that is suitable to screen the behaviour and functional communication development of children. Eligibility will also be determined based on children's performance on the PLS Screener, a direct screening assessment of language skills that is suitable to complete with children from birth to 8 years of age. The ASQ and PLS screener tools are both valid for the target sample of the current study. Parents of multilingual children will also be interviewed with questions from the BLEQ to establish the proportion of language exposure the child receives in all languages. The BLEQ will not be used to establish eligibility but will be used to gather information about the proportion of English and additional language exposure.

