8. STATISTICAL METHODS

8.1 SAMPLE SIZE ESTIMATION, JUSTIFICATION, AND CALCULATION

The sample size will be 24 Child-Educator dyads. A target of 12 dyads will be in Group A and 12 will be in Group B. This sample size is selected as a pragmatic threshold due to the likely enrolment of 24-28 educators per training period with an approximate 50% recruitment rate. A sample size larger than 24 dyads is not feasible for the context of the current study. This calculation also allows for dropout of 10% which is consistent with previous similar investigations. This sample size is also comparable to other similar studies in early childhood education (cf McDonald et al., 2015).

Previous data with comparable outcome measures was used to estimate the intra-class correlation (ICC) in a similar setting of educators grouped by centre. For most outcome measures, the ICC was estimated to be 0.1 or lower. Assuming two educators per centre (cluster), with six centres per treatment, a standard deviation in change score of 0.3 (Piastra et al., 2012; Berry-Kravis et al., 2013), an ICC of 0.1, alpha 0.05 and power 0.8, the study should be powered to detect a difference of 0.358. This is comparable to the difference in change score of 0.4 that was previously observed (Piastra et al., 2012).

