8.2 STATISTICAL METHODS TO BE UNDERTAKEN

All questionnaire data will be collected via Microsoft Teams and exported in raw format for processing in R or SPSS. Demographic information (including age, languages spoken, language proficiency, educator level of education, educator years of experience, and child communication measures [ASQ and PLS]) will be described for all dyad participants. Two multiple linear regression analyses will be conducted to address the primary aim (Stage 1 contrast) and our secondary aim (Stage 2 contrast). The outcome (dependent variable) for both analyses will be children's mean length of utterance Difference Score across each Stage. Independent variables will be Group allocation (A or B) and cluster (ECEC). This analysis plan will allow for the primary investigation to be conducted on data collected in Stage 1. This primary analysis will investigate the impact of group allocation (Training [Group A]; Control [Group B]) and cluster (Educator Centre) on children's language output (Mean Length of Utterance). The secondary investigation will be conducted on data collected in Stage 2. This secondary analysis will investigate the impact of group allocation (No-training follow-up [Group A]; Training [Group B]) and cluster (Educator centre) on children's language output.

Intention-to-treat analysis will be completed in the event of educator drop-out from the training. If appropriate, per-protocol analysis will be completed to investigate the primary and secondary outcomes.

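### The Stage 1 MLU change score is modelled on group and centre alone; adding Time 2 MLU as a covariate would improve precision unless the pre-post correlation is high, and would remove the shift caused by chance baseline imbalance

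*Protocol*

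**What the plan says.** Section 5.4 defines the outcomes as change: "A difference score for each outcome measure will be calculated for each stage of training". Difference Score 1 is Time 3 minus Time 2, and Difference Score 2 is Time 5 minus Time 4.

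Section 8.2 carries this into the model: "The outcome (dependent variable) for both analyses will be children's mean length of utterance Difference Score across each Stage". The predictors are then listed: "Independent variables will be Group allocation (A or B) and cluster (ECEC", and the list ends there. Age and other demographic data "will be described for all dyad participants", with no role in the model. The regressions in 8.2 are for MLU; no model is written for the educator composite.

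Section 6.2.2 admits children "aged 24-42 months and attend the consenting educator's ECEC at least one day per week". Section 8.1 states "The sample size will be 24 Child-Educator dyads" and "A target of 12 dyads will be in Group A and 12 will be in Group B", planned as six centres of two educators per group. Section 6.2.1 adds: "Group comparisons will be conducted at baseline to ensure homogeneity in group variability based on level of Education". Under section 5.8, centres available for only one training period are not randomised.

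**The concern.** Because 8.2 lists the predictors, leaving out the baseline value is a stated choice and not a detail left for a later plan.

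Each MLU value comes from a single 15-minute recording, so some regression to the mean is to be expected. Children who happen to score high at Time 2 will tend to gain less by Time 3, whatever their educator does. If one group starts higher by chance, its mean change is pulled down, and a model with only group and centre cannot allow for this. The same unexplained variation widens the confidence interval.

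Section 8.1 says that more than 24 dyads is not feasible, so any further precision has to come from the analysis. The covariate needed is already measured. The comparison on educator education in 6.2.1 does not help: with 12 dyads against 12 it can describe the groups but cannot make them alike, and it changes no estimate.

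**Working it through.** **Inputs.** From 8.1: 12 dyads per group, two per centre, six centres per group, SD of change 0.3, ICC 0.1, alpha 0.05, power 0.8, detectable difference 0.358. Assumed, because the protocol gives no value: r = 0.3, 0.5, 0.7 or 0.9; equal variance σ² before and after; the same ICC at baseline; two-sided alpha.

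**1. The protocol's figure.** Design effect = 1 + (2−1)×0.1 = 1.1. SE = 0.3×√(2×1.1/12) = 0.1285. Detectable difference = 0.1285×(1.960+0.842) = 0.360, against the stated 0.358. Power at 0.358 is 79.6%. The formula is not stated; a t calculation with 22 df and no design effect gives 0.359, so it cannot be told which was used. With the design effect and centre-level t (12 centres, 10 df) the figure is 0.399.

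**2. Variance with baseline adjustment.** Var(change) = 2σ²(1−r). Var(adjusted) = σ²(1−r²). Ratio = (1−r)(1+r)/[2(1−r)] = (1+r)/2. The detectable difference is multiplied by the square root of this ratio; the t columns also charge the lost degrees of freedom.

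| r | (1+r)/2 | Square root | Normal approximation (from 0.360) | Centre-level t, baseline, 9 df (from 0.399) | Baseline and age, 8 df, no credit for age |
|---|---|---|---|---|---|
| 0.3 | 0.65 | 0.806 | 0.290 | 0.326 | 0.331 |
| 0.5 | 0.75 | 0.866 | 0.312 | 0.350 | 0.356 |
| 0.7 | 0.85 | 0.922 | 0.332 | 0.373 | 0.379 |
| 0.9 | 0.95 | 0.975 | 0.351 | 0.394 | 0.401 |

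On the normal approximation, power for a difference of 0.30 rises from 64.6% to 82.6%, 76.9%, 71.7% and 66.9% respectively.

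**3. Check by simulation.** The formula treats the baseline slope as known. In 4,000 simulated trials per value of r (12 centres of two), the ratio of the adjusted to the change-score standard error was 0.83, 0.89, 0.96 and 1.00 with a dyad-level covariate. With centre means it was 0.1091/0.127 = 0.86, 0.1174/0.1275 = 0.92, 0.1255/0.1261 = 1.00 and 0.1339/0.130 = 1.03. The gain is therefore somewhat smaller than the table suggests.

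**4. Effect of a chance imbalance.** Given a baseline difference D between groups, the change-score estimate shifts by −(1−r)D. With the SD of change fixed at 0.3, σ = 0.3/√(2(1−r)), and one standard error of D is σ×√(2×1.1/12).

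| r | σ | One SE of D | Size of shift, (1−r)×SE | Share of 0.358 |
|---|---|---|---|---|
| 0.3 | 0.254 | 0.109 | 0.076 | 21% |
| 0.5 | 0.300 | 0.128 | 0.064 | 18% |
| 0.7 | 0.387 | 0.166 | 0.050 | 14% |
| 0.9 | 0.671 | 0.287 | 0.029 | 8% |

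Simulated slopes of the change-score estimate on D were −0.70, −0.48, −0.28 and −0.09. For the baseline-adjusted estimate they lay between −0.004 and 0.028, that is, about zero.

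**5. Stage 2.** With equal variances and equal correlations, cov(T5−T4, T2) = (r−r)σ² = 0, so adjusting Difference Score 2 for the Time 2 value gains nothing.

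**The case against.** The strongest reply is that the plan is coherent. The questions in 5.1 ask about the magnitude of change, the outcome is change, and 8.1 uses an SD of change. Comparing change scores is a legitimate analysis and, under randomisation, unbiased on average. All of that stands: this is an avoidable loss of efficiency and not an invalid analysis. The reply does not remove the shift conditional on the imbalance actually observed, and the same question can be answered with the baseline in the model.

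It is also fair that the size depends on a correlation that the protocol does not give, and that covariates are not free with about 10 centre-level degrees of freedom. At r = 0.9 the baseline-and-age model gives 0.401 against 0.399 unadjusted, if age explains nothing.

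Four stronger readings are tempting but not supported:

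- A reader might infer that baseline imbalance is left wholly uncorrected. It is not: subtraction corrects for it, and over-corrects by the fraction 1−r.
- A reader might infer that adjustment would remove bias from the non-randomised centres in 5.8. With a noisy covariate and systematic group differences it can under-adjust, and it does nothing for unmeasured differences.
- A reader might extend the remedy to Stage 2 by adjusting for Time 2. Sections 6.1.2 and 7.4 allow replacements between stages, who have no Time 2 value. The adjustment gains nothing for Difference Score 2 under equal correlations. Modelling Time 5 alone would change the question in 5.1.1.1.
- A reader might apply the criticism to every outcome. The model in 8.2 covers MLU only; a model for the educator composite may stand in an analysis plan that is not at hand.

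Nor does 6.2.1 say that its comparison is a significance test. The narrower point is that no comparison of this kind can ensure homogeneity.

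**Conclusion.** The point holds for the primary Stage 1 analysis of MLU. As specified, that analysis is valid but weaker than it need be, in a trial that cannot recruit more dyads. By formula, baseline adjustment would lower the detectable difference by about 19% at r = 0.3, 13% at 0.5, 8% at 0.7 and 3% at 0.9 (one minus the square roots above). With the baseline slope estimated at dyad level, the simulated reductions in standard error are about 17%, 11%, 4% and nil. A one-standard-error chance imbalance moves the change-score estimate by 8% to 21% of the stated detectable difference over the same range.

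These figures rest on an assumed r, equal variances, an ICC of 0.1 and the planned 12 centres of two. The further gain from child age cannot be computed from the protocol. The change is worth making; it does not turn the comparison into a fully randomised one.

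**What to change.** In section 8.2, for the primary Stage 1 comparison, prespecify Time 2 MLU as a covariate, with either Time 3 MLU or Difference Score 1 as the outcome; with the baseline in the model, the group estimate is the same. Child age at Time 2 may be named as a second covariate if wanted. Handle centre as clustering, by a random intercept or a centre-level analysis with small-sample degrees of freedom. Entering centre as an ordinary predictor beside group, when each centre belongs to one group, is a separate problem that the same edit can settle. If the educator composite is modelled, use its own Time 2 value in the same way.

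Do not add a Time 2 adjustment to Stage 2. In 6.2.1, call the comparison on education descriptive and drop the claim that it ensures homogeneity.

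State beside the model that adjustment deals with chance imbalance in the measured baseline and does not cure confounding from the non-randomised centres.

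The cost is a sentence or two of text and one or two of about 10 centre-level degrees of freedom. No new data are needed. If r is near 0.9, little or nothing is gained, and with age added there may be a slight loss.

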5.8 RANDOMISATION

Centres participating in the Training will indicate availability for either or both of the training periods. We will use the random number generator at <https://www.random.org/integers/> to allocate centres who indicate availability for both stages. Therefore, pseudo-cluster randomisation will be implemented, as centres who are available in one time period only will not be randomised for pragmatic reasons. Randomisation will occur at the cluster or centre level to avoid cross-contamination effects between trained and untrained educators. This will occur after educators and children have been recruited in to the current study. This pseudo-randomization is required for the current, pragmatic study.

Masking of educators to training (+training) and no training (-training) conditions is not possible as they are actively participating in the training. The speech pathologist who analyses interaction skills will be blinded to which time point the video is recorded in and the condition that the educator is assigned to (+ training or –training). Therefore, this is a single blinded study.

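### Videos are allocated to coders one by one, so about half the dyads change coder within a stage, which adds avoidable noise of unknown size to the educator change score

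*Protocol*

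**What the plan says.** Protocol section 5.4 describes how the eight educator strategies are scored. Each is marked absent or present in every 30-second segment of a 15-minute video and averaged over segments. "Then, all average scores will be summed to create a composite score of use of interaction strategies by educators". The endpoint is a change: "The primary outcome measure for educators will be the change in the composite score of overall interaction strategies". The same section sets the time frame: "A difference score for each outcome measure will be calculated for each stage of training", that is, Time 3 against Time 2 and Time 5 against Time 4. The secondary educator outcomes are differences in the individual strategy scores from the same coding.

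Two team members code. For calibration, "These two members will score two video samples independently and meet to reach consensus". After that, "The remaining video samples will be randomly allocated and coded by one of these two researchers", and "each of the two researchers will code 50% of the video samples each". The unit that is allocated is the single video. Nothing keeps the videos of a dyad, or of a stage, with one coder. The check on agreement is: "Inter- and intra-rater reliability will be calculated based on 10% of the recorded samples". No threshold or consequence is attached to it.

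Section 5.8 adds the masking: "The speech pathologist who analyses interaction skills will be blinded to which time point the video is recorded in", and likewise to the educator's condition. It speaks of one coder where section 5.4 names two.

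**The concern.** If one coder marks strategies present a little more readily than the other, that lean cancels from a before/after difference only when the same coder scores both videos. When coders are drawn video by video, it stays in the difference for every dyad whose coder changes. Several strategies call for judgement (waiting expectantly, responding with animation), so some systematic difference between coders is plausible.

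What is at stake is precision on one of the two primary outcomes and on the secondary strategy scores. Section 8.1 states that more than 24 dyads is not feasible, so lost precision cannot be bought back with sample size.

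**Working it through.** **Inputs from the protocol.** 24 dyads, 12 per group, as two educators in each of six centres per group; SD of change 0.3; ICC 0.1; alpha 0.05 (taken as two-sided); power 0.80; stated detectable difference 0.358 (section 8.1). Four videos per dyad (section 5.6.2), so 24 × 4 = 96 videos, or 94 after the two calibration videos if those are study videos. Half are coded by each researcher (section 5.4).

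**Assumed, not in the protocol.** The severity difference d in composite points; that 0.3 is the SD of the composite's change; and that this SD contains no coder noise.

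**Step 1: the protocol's own figure.** The design effect is 1 + (2 − 1) × 0.1 = 1.10. The detectable difference is (1.960 + 0.842) × 0.3 × √(2 × 1.10/12) = 0.360, against the stated 0.358. Power at 0.358 by the same normal approximation is 79.6%. The figure is reproduced.

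**Step 2: how often the coder changes.** With 94 videos split 47/47, the chance that a dyad's two videos in a stage have different coders is 47/93 = 0.505 (48/95 = 0.505 for 96 videos). That is about 12 of 24 dyads. In simulated allocations the share had a 95% range of 30% to 71%.

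**Step 3: variance added.** A dyad with one coder receives 0. A dyad with two coders receives +d or −d with equal probability. The mean is 0 and the added variance is 0.505 × d², about d²/2. If one coder scores both videos, it is 0.

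**Step 4: what d means.** A 15-minute video has 30 segments, so there are 30 × 8 = 240 coded cells, each worth 1/30 on the 0–8 composite. A d of 0.1, 0.2 or 0.3 is a net difference of 3, 6 or 9 cells out of 240.

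**Step 5: effect at SD 0.3.** Coder noise is not clustered by centre, so the design effect applies only to the original variance: detectable difference = 2.802 × √[2 × (0.09 × 1.10 + 0.505 d²)/12]. Power is at the difference that has 80% without coder noise (0.360); using 0.358 changes it by less than one point.

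| d | added variance | SD of change | detectable difference | power | dyads needed to offset |
|---|---|---|---|---|---|
| 0.05 | 0.0013 (1.4%) | 0.302 | 0.362 | 79.5% | 24.3 |
| 0.1 | 0.0051 (5.6%) | 0.308 | 0.369 | 78% | 25.2 |
| 0.2 | 0.0202 (22.5%) | 0.332 | 0.395 | 72% | 28.9 |
| 0.3 | 0.0455 (50.5%) | 0.368 | 0.435 | 64% | 35.0 |

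**Step 6: if the composite's SD is larger.** Power is again at the difference that would have had 80% at that SD. At SD 0.6, d = 0.2 leaves 78% and d = 0.4 leaves 72%. At SD 1.0, d = 0.5 leaves 76%.

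**The case against.** The strongest objection is that the size is unknown. Calibration to consensus on two videos may bring the coders close together, leanings in opposite directions on different strategies partly cancel in a sum of eight, and at d = 0.05 almost nothing is lost. Section 8.1 does not tie the SD of 0.3 to the composite, and a larger SD shrinks the loss. All of this stands. It limits the size of the loss but not the mechanism: calibration and a reliability figure may reduce or describe a severity difference, but they do not take it out of the change score.

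The second objection is masking. A coder who always sees the same dyad more than once may find the time point easier to guess, and that could exchange harmless noise for expectation bias. This stands as a small downside. Under the present rule one coder already scores both videos of a stage for about half the dyads, and mixed, unlabelled order limits the risk.

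A reader might infer more than the text supports:

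- **Bias.** Random allocation makes the coder error independent of group in expectation. A chance imbalance in one realised allocation is the same variance seen another way, and not a second harm.
- **A coder term missing from the planned model.** Both regressions in section 8.2 have the child's mean length of utterance as outcome. No model for the educator composite is stated there, and a statistical analysis plan that is not shown may supply one.
- **The same fault in mean length of utterance.** The two-coder rule in section 5.4 covers interaction strategies only. No division of transcription between people is described.

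**Conclusion.** The concern holds as a point about efficiency. Allocation by single video does not suit an endpoint defined as a within-dyad change: about half the dyads will have two coders within a stage, and each such change score carries the coders' severity difference in full.

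The cost lies between negligible and material. On the assumptions that the 0.3 is the composite's change SD and is free of coder noise, it runs from under one point of power at d = 0.05 to about 16 points at d = 0.3. With a larger SD it is smaller. If the 0.3 already contains coder noise, the planned power is not reduced, and same-coder scoring would improve on it instead. The protocol does not settle which case applies, so no single power figure should be quoted as the trial's power. The change is worth making because it is nearly free and the sample size is fixed.

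**What to change.** In section 5.4, replace the sentence that allocates the remaining videos with:

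> Dyads are randomly allocated to the two researchers, balanced within Group A and Group B; all videos of a dyad are coded by the same researcher, in random order mixed with the videos of other dyads and without time-point or group label.

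This brings the variance added by a constant severity difference to zero and keeps the half-and-half workload and the masking in section 5.8. It does not remove drift within a coder or error in single segments. The cost is one sentence and a different allocation list, plus the small masking downside described above. In the same edit, section 5.8 should be brought into line with section 5.4 on the number of coders.
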